## **Ovarian Response and Extreme Ovarian Response**

The ovarian response will be defined based on the number of oocytes retrieved, and if the cycle was cancelled, the reason for cycle cancellation. Subjects will be grouped according to ovarian response as:

- Low response (<4 oocytes retrieved or cancellation of cycle due to poor ovarian response)
- Moderate response (4-7 oocytes retrieved)
- Targeted response (8-14 oocytes retrieved)
- Hyperresponse (15-19 oocytes retrieved)
- Severe hyperresponse ( $\geq 20$  oocytes retrieved or cancellation of cycle due to excessive ovarian response)

Extreme ovarian response will be defined as:

- <4 oocytes retrieved or cancellation of cycle due to poor ovarian response
- $\geq 15$  oocytes retrieved or cancellation of cycle due to excessive ovarian response
- $\geq 20$  oocytes retrieved or cancellation of cycle due to excessive ovarian response
- <4 or  $\geq 15$  oocytes retrieved or cancellation of cycle due to poor or excessive ovarian response
- <4 or  $\geq 20$  oocytes retrieved or cancellation of cycle due to poor or excessive ovarian response

For each definition of ovarian response and extreme ovarian response the proportion of subjects will be tabulated. Treatments will be compared using a logistic regression model with treatment and age stratum as factors. The difference between treatments will be reported as an odds ratio including 95% confidence interval and p-value for test of no treatment difference. If the expected number of observations is less than five in any of the cells in the contingency table then Fisher's exact test will be used as alternative. The possibility of a treatment-by-age interaction will be investigated.

#### **Cycle Cancellation due to Poor or Excessive Ovarian Response or Embryo Transfer Cancellation due to Excessive Ovarian Response / OHSS Risk**

The number of subjects with cycle cancellation or embryo transfer cancellation including the reasons for cancellation will be summarised.

The following endpoints will be defined:

- Cycle cancellation or embryo transfer cancellation
- Cycle cancellation due to poor or excessive response, or transfer cancellation due to excessive ovarian response/OHSS risk
- Cycle cancellation due to poor ovarian response
- Cycle cancellation due to excessive ovarian response
- Cycle cancellation due to poor or excessive ovarian response
- Transfer cancellation due to excessive ovarian response/OHSS risk
- Cycle cancellations due to excessive response or transfer cancellation due to excessive ovarian response/OHSS risk

These endpoints will be tabulated and analysed in a similar manner as extreme ovarian response.

## **Number and Size of Follicles during Stimulation**

Based on the transvaginal ultrasound on stimulation day 6 and at end-of-stimulation the following endpoints are defined:

- Total number of follicles
- Size of the largest follicle (mm)
- Average follicle size (mm)
- Average size of three largest follicles (mm)
- Number of follicles  $\geq 8$  mm,  $\geq 10$  mm,  $\geq 12$  mm,  $\geq 15$  mm and  $\geq 17$  mm

Number and size of follicles will be compared between treatments using the van Elteren test stratified for age and within each age stratum using the Wilcoxon's test.

The follicle cohort on stimulation day 6 and end-of-stimulation will be summarised on the follicle level (number of follicles 2-7 mm, 8-9 mm, 10-11 mm, 12-14 mm, 15-16 mm and  $\geq 17$  mm).

## **Number of Oocytes Retrieved**

The number of oocytes retrieved will be compared between treatments using the van Elteren test stratified for age and within each age stratum using the Wilcoxon's test.

Additional summarises will be made for subjects with at least one oocyte retrieved. The purpose of this is purely descriptive.

## **Metaphase II Oocytes**

Oocytes undergoing ICSI will have their maturity stage assessed prior to insemination. The percentage of MII oocytes to oocytes retrieved for subjects where all oocytes are inseminated using ICSI will be tabulated. In the subgroup of subjects where all oocytes are inseminated using ICSI the number of MII oocytes will be compared between treatments using the van Elteren test stratified for age and within each age stratum using the Wilcoxon's test. Subjects will be grouped according to number of MII oocytes as:  $\leq 6$ , 6-12,  $\geq 13$  and the corresponding frequencies tabulated.

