## **Metaphase II Oocytes**

Oocytes undergoing ICSI will have their maturity stage assessed prior to insemination. The percentage of MII oocytes to oocytes retrieved for subjects where all oocytes are inseminated using ICSI will be tabulated. Further, the number of MII oocytes per subject will be tabulated including both summary statistics and a frequency table. Continuous data will be compared between treatment groups using the van Elteren test stratified for age-group. Ordinal data will be compared using the Cochran-Mantel-Haenszel test for ordinal data stratified for age-group. Within strata comparisons will be based on Wilcoxon's test.

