#### Secondary Endpoints

- Positive  $\beta$ hCG rate (positive serum  $\beta$ hCG test 13-15 days after transfer)
- Clinical pregnancy rate (at least one gestational sac 5-6 weeks after transfer)
- Vital pregnancy rate (at least one intrauterine gestational sac with fetal heart beat 5-6 weeks after transfer)
- Implantation rate (number of gestational sacs 5-6 weeks after transfer divided by number of embryos transferred)
- Ongoing implantation rate (number of intrauterine viable fetuses 10-11 weeks after transfer divided by number of embryos transferred)
- Proportion of subjects with extreme ovarian responses, defined as  $<4$ ,  $\geq 15$  or  $\geq 20$  oocytes retrieved
- Proportion of subjects with early OHSS (including OHSS of moderate/severe grade) and/or preventive interventions for early OHSS

- Proportion of subjects with cycle cancellation due to poor or excessive ovarian response or embryo transfer cancellation due to excessive ovarian response / OHSS risk
- Number and size of follicles on stimulation day 6 and end-of-stimulation
- Number of oocytes retrieved and proportion of subjects with <4, 4-7, 8-14, 15-19 and ≥20 oocytes retrieved
- Percentage of metaphase II oocytes (only applicable for those inseminated using ICSI), fertilisation rate as well as number and quality of embryos on day 3 after oocyte retrieval
- Circulating concentrations of LH, estradiol, progesterone, inhibin A and inhibin B on stimulation day 6 and end-of-stimulation
- Circulating concentrations of FSH on stimulation day 6, end-of-stimulation and oocyte retrieval as well as FSH population pharmacokinetic parameters
- Total gonadotropin dose and number of stimulation days
- Proportion of subjects with investigator-requested gonadotropin dose adjustments
- Frequency and intensity of adverse events
- Changes in circulating levels of clinical chemistry and haematology parameters and proportion of subjects with markedly abnormal changes
- Frequency and intensity of injection site reactions (redness, pain, itching, swelling and bruising) assessed by the subject during the stimulation period
- Proportion of subjects with treatment-induced anti-FSH antibodies, overall as well as with neutralising capacity
- Frequency and intensity of immune-related adverse events
- Proportion of subjects with cycle cancellations due to an adverse event, including immune-related adverse events, or due to technical malfunctions of the administration pen

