## **Fertilisation Rate**

An oocyte is defined as fertilised if it is scored as 2 pronuclei on day 1 after oocyte retrieval. For subjects with oocytes retrieved, the rate of fertilised oocytes to oocytes retrieved (and also the rate of fertilised oocytes to metaphase II oocytes for those inseminated using ICSI) will be tabulated. The number of fertilised oocytes and the fertilisation rate will be compared between treatment groups using the van Elteren test stratified for age and within each age stratum using the Wilcoxon's test. Subjects will be grouped according to number of fertilised oocytes as: <4, 4-7, 8-14, 15-19,  $\geq 20$  and the corresponding frequencies tabulated. Note that the analysis of fertilisation rates excludes subjects without oocytes retrieved and do therefore not adhere to the randomisation principle.

## Number and Quality of Embryos on Day 3

Based on the embryo assessment day 3 the following endpoints are defined:

- Number of embryos
- Number of good-quality embryos
- Subjects with at least one embryo
- Subjects with at least one good-quality embryo
- Rate of embryos to oocytes retrieved
- Rate of good-quality embryos to oocytes retrieved
- Rate of embryos to MII oocytes
- Rate of good-quality embryos to MII oocytes
- Number of cryopreserved embryos
- Subjects with at least one cryopreserved embryo

Numbers and rates will be compared between treatments using the van Elteren test stratified for age and within each age stratum using the Wilcoxon's test. For each definition of 'subjects with at least one' the proportion of subjects will be tabulated and analysed in a similar manner as extreme ovarian response.

Embryo quality will be summarised including a breakdown by selected quality parameters (degree of fragmentation, embryo stage, blastomere uniformity, visual sign of multi-nucleation) and insemination method. Separate summaries will be made for the transferred embryos and for the cryopreserved embryos.

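### The named secondary endpoint, the percentage of metaphase II oocytes, has no treatment comparison in the SAP; only the number of MII oocytes is tested

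*SAP*

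**What the plan says.** The endpoint is worded identically in Protocol 2.2 and SAP 2.2: "Percentage of metaphase II oocytes (only applicable for those inseminated using ICSI").

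SAP 9.3, Metaphase II Oocytes, treats two quantities differently:
- The percentage is described only: "The percentage of MII oocytes to oocytes retrieved for subjects where all oocytes are inseminated using ICSI will be tabulated".
- The count is tested, by van Elteren stratified for age and Wilcoxon within stratum: "In the subgroup of subjects where all oocytes are inseminated using ICSI the number of MII oocytes will be compared between treatments".

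Protocol 9.7.3, Metaphase II Oocytes, tabulates first the percentage and then the count, and adds a general sentence: "Continuous data will be compared between treatment groups using the van Elteren test stratified for age-group".

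The neighbouring paragraphs of SAP 9.3 test both kinds of quantity. For fertilisation: "The number of fertilised oocytes and the fertilisation rate will be compared between treatment groups using the van Elteren test". For day 3 embryos: "Numbers and rates will be compared between treatments using the van Elteren test stratified for age". Yield is tested in its own right: "The number of oocytes retrieved will be compared between treatments using the van Elteren test stratified for age".

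The opening of SAP 9.3 says that the FAS analysis of each secondary endpoint serves to judge whether the treatments differ significantly. SAP 12, on changes from the protocol, does not mention the MII percentage.

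**The concern.** The percentage asks whether the oocytes obtained are mature. The count asks how many mature oocytes were obtained, which depends heavily on how many were retrieved. Protocol 3.5.2 lists oocyte and embryo quality separately from oocytes retrieved, so maturity is meant to be a question of its own. FE 999049 dosing can be expected to influence yield: Protocol 1.1 reports a significant dose-response on oocytes retrieved in both phase 2 trials, and fewer extreme responses than with GONAL-F in ESTHER-1.

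With the test on the count, a true difference in maturity is hard to see against the variation in yield, and a difference in yield alone moves the result. At stake is what the report can say about oocyte maturity.

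**Working it through.** **Text.** Set side by side, the three parallel endpoints read as follows.

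| Endpoint (SAP 9.3) | Number tested | Rate or percentage tested |
|---|---|---|
| MII oocytes | yes | no, tabulated only |
| Fertilised oocytes | yes | yes |
| Day 3 embryos | yes | yes |

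MII is the exception, and it is the one whose named endpoint is explicitly a percentage.

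**Size.** Neither document states a power, effect size or sample size for this endpoint, so there is no figure to reproduce. The ICSI share, mean oocyte count and maturity rate are not given either. The following are therefore assumptions:
- mean of about 10 oocytes, SD 5.5;
- maturity 78% in one arm and 73% in the other;
- within-woman correlation of maturity 0.05;
- age strata of 70, 18 and 12%;
- 100, 200 or 300 all-ICSI women per arm. With 1,000 / 2 = 500 randomised per arm, that is 20 to 60%.

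*Hand check.* MII number = oocytes retrieved × share mature.
- Count: 10 × 0.78 − 10 × 0.73 = 7.8 − 7.3 = 0.5 oocytes. Variation in yield alone gives the count an SD of 0.78 × 5.5 = 4.29, so the standardised difference is at most about 0.5 / 4.29 = 0.12.
- Percentage, for a woman with 10 oocytes: SD = √[0.78 × 0.22 × (0.05 + 0.95/10)] = √(0.1716 × 0.145) = 0.158, so the standardised difference is 0.05 / 0.158 = 0.32.

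The same maturity difference is much larger relative to its noise on the percentage scale. Women with fewer oocytes have noisier percentages, so power was taken from simulation.

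*Simulation.* 2,000 trials per scenario, van Elteren test over three age strata, two-sided 5%. Rejection rates:

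| Scenario | Variable tested | 100 per arm | 200 per arm | 300 per arm |
|---|---|---|---|---|
| Maturity 73 v 78%, equal yield | number | 12% | 19% | 26% |
| | percentage | 48% | 77% | 91% |
| Yield 11.5 v 10, maturity 78% in both | number | 47% | 78% | 92% |
| | percentage | 5% | 5% | 6% |
| No difference | either | about 4 to 6% | about 4 to 6% | about 4 to 6% |

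A second set of assumptions (SD 6, correlation 0.08, maturity 70 v 75%, equal mean yield of 10, unstratified test) gives the same picture at 150 and 300 per arm: number 15% and 24%, percentage 55% and 85%.

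**The case against.** The strongest opposing case has four parts.

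1. *The endpoint is still reported, and yield is tested alongside it.* A reader might infer that a yield effect will pass for a maturity difference. The documents do not support going that far. The tested variable is plainly labelled a number, the percentage is tabulated by arm in the same paragraph, and yield has its own test in the paragraph before. In the yield-only scenario a significant count result correctly detects more MII oocytes; it is not a false positive. With 10 v 11 oocytes and 75% maturity in both arms, at 150 and 300 per arm, the count test rejects in 30% and 51% of trials and the yield test in 36% and 58%, so the cause would often show beside the result. This stands, with one reservation: the yield test is not confined to the all-ICSI subgroup, so the two results are not on the same women.

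2. *Nothing was clearly dropped.* A reader might infer that the SAP silently removed a test that the protocol had planned. The general sentence in Protocol 9.7.3 can equally refer to the count alone, because that section describes summary statistics and a frequency table only for the count. The SAP's own handling of fertilisation and embryos, where the protocol uses the same sentence, favours the wider reading, but it remains an inference.

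3. *Other tests touch on maturity.* SAP 9.3 tests fertilisation rate and embryo rates, some of them per MII oocyte. Rates per retrieved oocyte would fall if maturity fell, but only indirectly. Rates per MII oocyte describe what follows maturation. None of them tests the named endpoint.

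4. *The size depends on the scenario.* If the less mature arm also has the lower yield (9.3 v 10, maturity 70 v 75%), the two tests perform alike: number 47% and 75%, percentage 49% and 78% at 150 and 300 per arm. Exact cancellation of yield and maturity needs tuned inputs and should not be used as the headline. The lower rate of extreme responses in ESTHER-1 does not establish a shift in mean yield. This also stands.

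**Conclusion.** The point holds, as a minor one. The named endpoint has no planned treatment comparison, which does not fit the general statement opening SAP 9.3 or the treatment of the two parallel endpoints. The variable that is tested mixes yield with maturity.

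At equal yield, and under assumed inputs that the documents do not supply, the count test detects a 5-point maturity difference in roughly 12 to 26% of trials and the percentage test in roughly 48 to 91%. The direction at equal yield follows from the arithmetic; the size depends on oocyte count, maturity, the number of all-ICSI women and whether yield also differs.

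The consequence is confined to what can be said about oocyte maturity. The endpoint is not among the supportive pregnancy endpoints, no secondary endpoint is adjusted for multiplicity (SAP 9.1), and the non-inferiority conclusion on ongoing pregnancy is untouched.

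**What to change.** In SAP 9.3, Metaphase II Oocytes:
- Add the percentage of MII oocytes among oocytes retrieved to the age-stratified van Elteren test and the within-stratum Wilcoxon tests. Restrict it to women with at least one oocyte retrieved and all oocytes inseminated by ICSI. The ICSI restriction is essential: maturity is assessed only for oocytes undergoing ICSI (Protocol 7.2.11), so the percentage is undefined for IVF women and understated where insemination is mixed.
- Keep the number of MII oocytes as an additional comparison.
- Repeat the caveat already attached to fertilisation rate, that a comparison limited to such a subgroup is not protected by randomisation.

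The cost is a sentence or two of text and one further test on data that are already collected and tabulated. If the sponsor prefers to leave the percentage descriptive, SAP 12 should say so and give the reason.

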## **Fertilisation Rate**

An oocyte is defined as fertilised if it is scored as 2 pronuclei on day 1 after oocyte retrieval. For subjects with oocytes retrieved, the rate of fertilised oocytes to oocytes retrieved (and also the rate of fertilised oocytes to metaphase II oocytes for those inseminated using ICSI) will be tabulated. The number of fertilised oocytes and the fertilisation rate will be compared between treatment groups using the van Elteren test stratified for age and within each age stratum using the Wilcoxon's test. Subjects will be grouped according to number of fertilised oocytes as: <4, 4-7, 8-14, 15-19,  $\geq 20$  and the corresponding frequencies tabulated. Note that the analysis of fertilisation rates excludes subjects without oocytes retrieved and do therefore not adhere to the randomisation principle.

## Number and Quality of Embryos on Day 3

Based on the embryo assessment day 3 the following endpoints are defined:

- Number of embryos
- Number of good-quality embryos
- Subjects with at least one embryo
- Subjects with at least one good-quality embryo
- Rate of embryos to oocytes retrieved
- Rate of good-quality embryos to oocytes retrieved
- Rate of embryos to MII oocytes
- Rate of good-quality embryos to MII oocytes
- Number of cryopreserved embryos
- Subjects with at least one cryopreserved embryo

Numbers and rates will be compared between treatments using the van Elteren test stratified for age and within each age stratum using the Wilcoxon's test. For each definition of 'subjects with at least one' the proportion of subjects will be tabulated and analysed in a similar manner as extreme ovarian response.

Embryo quality will be summarised including a breakdown by selected quality parameters (degree of fragmentation, embryo stage, blastomere uniformity, visual sign of multi-nucleation) and insemination method. Separate summaries will be made for the transferred embryos and for the cryopreserved embryos.

## Circulating Levels of Endocrine Parameters

Blood samples drawn at stimulation days 1 and 6 and end-of-stimulation are analysed for FSH, LH, estradiol, progesterone, inhibin A and inhibin B. Furthermore, blood samples drawn at the oocyte retrieval visit are also analysed for FSH. Values below the lower limit of quantification (LLOQ) will be included as LLOQ/2. Values above the upper limit of quantification (ULOQ) will be included as ULOQ.

Each endocrine parameter and the change from baseline for post-baseline measurements will be tabulated for stimulation day 1 (baseline), stimulation day 6 and end-of-stimulation (and also the oocyte retrieval visit for FSH). For each parameter the change from baseline will be compared between treatments using an analysis of covariance model (ANCOVA). The ANCOVA will be fitted to the relative change from baseline in ln-transformed measurements with treatment and age stratum as fixed factors and the ln-transformed baseline measurement as covariate. The estimated treatment difference with 95% confidence interval will be presented on the scale of measurement (i.e. back-transformed using base e) and accompanied by the p-value for test of no treatment difference.

Summary tables will be prepared for LH and/or progesterone displaying the proportion of subjects who have a markedly abnormal value. These tables will also include a break-down by classification of the baseline value. The markedly abnormal criteria is specified in Appendix 1.

#### **9.4 Other Endpoints**

##### **FSH Population Pharmacokinetics**

A population pharmacokinetic model describing FSH concentrations following repeated dosing of FE 999049 will be prepared under the responsibility of the Ferring Translational Medicine Department.

These results will be reported separately.

### **10 Safety**

#### **10.1 General Considerations**

Safety endpoints will be summarised by treatment group for the safety analysis set. Separate tables will be produced by country.

##### **Missing Data**

For adverse events a worst-case approach will be used to impute missing values for causality, intensity and seriousness of the event.

#### **10.2 Adverse Events**

Adverse events will be coded using MedDRA. The version of MedDRA will be documented.

Adverse events are grouped according to start of IMP as follows:

- Pre-treatment adverse event, i.e. any adverse event occurring after signed informed consent and before start of IMP, or a pre-existing medical condition that worsens in intensity after signed informed consent but before start of IMP.
- Treatment-emergent adverse event, i.e. any adverse event occurring after start of IMP and before the end-of-trial visit, or a pre-treatment adverse event or pre-existing medical condition that worsens in intensity after start of IMP and before the end-of-trial visit.

If the timing of an AE cannot be established in relation to the administration of IMP, it will be considered as a treatment emergent AE.

In addition to the grouping of adverse events described in the protocol, adverse events will be categorised as 'other significant adverse events' and 'unexpected non-serious adverse drug reactions'. These events will be identified in a blinded review of the data before declaration of clean file and lock of database.

Treatment-emergent adverse events will be presented in summary tables and listings. Pre-treatment adverse events will be presented in listings only.

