### **6.7 Clinical Pregnancy**

Subjects with a positive  $\beta$ hCG test must attend a visit 5-6 weeks after transfer.

The following must take place:

- Transvaginal ultrasound of uterus to assess any clinical pregnancy
- Drug accountability of progesterone
- Dispensing of progesterone for luteal phase support, if continued according to local practice
- Recording of use of any concomitant medication
- Recording of adverse events

If at least one gestational sac (either intrauterine or ectopic) is observed, this confirms a clinical pregnancy. If at least one intrauterine gestational sac with fetal heart beat is observed, this confirms a vital pregnancy. For subjects with a vital pregnancy, the next visit is the ongoing pregnancy visit 10-11 weeks after transfer (section 6.8). Subjects with no vital pregnancy must undergo end-of-trial assessments (section 6.9).

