## 6.9 End-of-trial

If a subject attends the scheduled trial visits, the end-of-trial assessments should take place at the last scheduled trial visit, i.e. for subjects with a confirmed vital pregnancy, the ongoing pregnancy visit would be the last scheduled trial visit and thus the visit where the end-of-trial assessments should be done.

Due to the timing of the mandatory anti-FSH antibody assessments, the end-of-trial assessments can at the earliest be 19-28 days after the last FE 999049 or GONAL-F dose. This may coincide with the  $\beta$ hCG visit for subjects with a negative  $\beta$ hCG test.

The following procedures / assessments must take place at the end-of-trial visit, irrespective of whether the subject discontinues the trial prematurely or completes it:

- Body weight
- Physical examination
- Gynaecological examination
- Vital signs
- Blood collection for central laboratory analysis of
  - clinical chemistry and haematology parameters
  - anti-FSH antibodies (second post-dosing assessment) [*note*: only applicable for subjects who have not already had a blood sample taken for the second post-dosing anti-FSH antibodies assessment as described in sections 6.6.1 and 6.6.2]
- Drug accountability, if applicable
- Recording of use of any concomitant medication
- Recording of adverse events
- Completion of end-of-trial form

These assessments serve to document the subject's physical health at the end of the trial.

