### **7.3.8 Physical Examination**

A complete physical examination will be performed at screening and end-of-trial. Information will be recorded for general appearance, central and peripheral nervous system, head and neck (including ears, eyes, nose, mouth and throat), respiratory system, cardiovascular system, gastrointestinal system, lymphatic system, urinary system, musculoskeletal system and skin.

At screening, each category will be evaluated as normal, abnormal not clinically significant or abnormal clinically significant. Abnormal clinically significant findings at screening must be reported on the Medical History Log.

At end-of-trial, potential changes from screening to end-of-trial will be evaluated for each category. In case of changes, these will be evaluated as normal, abnormal not clinically significant or abnormal clinically significant. Abnormal clinically significant changes from screening to end-of-trial must be recorded as adverse events.

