### **Date and Time of Onset**

The date of onset is the date when the first sign(s) or symptom(s) were first noted. If the adverse event is an abnormal clinically significant laboratory test or outcome of an examination, the onset date is the date the sample was taken or the examination was performed.

---

g Exception: if an adverse event with onset before the first IMP administration (i.e. a pre-treatment adverse event) changes in intensity after the administration of the IMP, this must be recorded as two separate events. The initial adverse event should be recorded with outcome “not yet recovered” and the date and time of outcome is when the intensity changed. The second adverse event should be recorded with date and time of onset when the intensity changed.

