### **10.2.2 Incidence of Adverse Events**

Treatment-emergent adverse events will be tabulated by system organ class (SOC) alphabetically and preferred term (PT) in decreasing order of frequency. The following will be presented: number of subjects reporting an adverse event, the percentage of subjects with an adverse event, and the number of events reported.

Summary tables will be produced for the following:

- All adverse events
- Adverse events by causality (reasonable possibility / no reasonable possibility)
- Adverse events leading to death
- Adverse events by intensity (mild / moderate / severe)
- Adverse drug reactions by intensity (mild / moderate / severe)
- Serious adverse events
- Adverse events leading to discontinuation
- Other significant adverse events
- Unexpected non-serious adverse drug reactions
- Adverse events with an incidence of  $\geq 5\%$  in any treatment group
- Non-serious adverse events with an incidence of  $\geq 5\%$  in any treatment group

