### **10.9 Multi-fetal Gestation, Biochemical Pregnancy, Spontaneous Abortion, Ectopic Pregnancy and Vanishing Twins**

The incidence of biochemical pregnancy, spontaneous abortion, ectopic pregnancy and vanishing twins will be reported as part of the adverse events summaries described in Section 10.2.2 .

Early pregnancy loss is defined as pregnancy loss occurring before ongoing pregnancy ( $\beta$ hCG to ongoing pregnancy). The incidence of early pregnancy loss will be tabulated. The denominator will be the subjects at risk for early pregnancy loss, i.e. number of subjects with a positive  $\beta$ hCG. Early pregnancy losses will also be grouped as: '  $\beta$ hCG to vital pregnancy' and 'vital pregnancy to ongoing pregnancy'. Summaries will be made overall, by vital pregnancy type and by ongoing pregnancy type. The pregnancy types are defined as 'singleton', 'twin', 'triplets' and 'higher-order multiples' based on number of intrauterine viable fetus(es) at the respective assessment.

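### The treatment-emergent window stops short of the end-of-trial visit, so events first found at that visit, vanishing twins above all, fall outside the SAP 10.2 adverse event tables and listings

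*SAP*

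**What the plan says.** - **Window.** SAP 10.2 counts as treatment-emergent "any adverse event occurring after start of IMP and before the end-of-trial visit". Protocol 9.7.3 (Adverse Events, General) uses the same words. The clause on worsening of earlier conditions closes at the same point.
- **Presentation.** SAP 10.2: "Treatment-emergent adverse events will be presented in summary tables and listings. Pre-treatment adverse events will be presented in listings only". SAP 10.2.2 then opens with "Treatment-emergent adverse events will be tabulated by system organ class (SOC) alphabetically". There is no third class.
- **Onset date.** Under protocol 8.2.2 (Date and Time of Onset), onset is normally the first sign or symptom. For a significant laboratory test or examination outcome, "the onset date is the date the sample was taken or the examination was performed".
- **End-of-trial visit.** For a confirmed vital pregnancy, protocol 6.9 says "the ongoing pregnancy visit would be the last scheduled trial visit and thus the visit where the end-of-trial assessments should be done". Otherwise protocol 6.7 applies: "Subjects with no vital pregnancy must undergo end-of-trial assessments". Section 6.9 places those assessments at the last scheduled visit.
- **Findings at that visit.** Protocol 7.3.8: "Abnormal clinically significant changes from screening to end-of-trial must be recorded as adverse events". Section 7.3.9 repeats this for the gynaecological examination. Section 8.1 covers laboratory and vital-sign findings judged clinically significant.
- **Pregnancy losses.** SAP 10.9 deals with four outcomes: vanishing twins, ectopic pregnancy, spontaneous abortion and biochemical pregnancy. On how often each occurs, it states that this "will be reported as part of the adverse events summaries described in Section 10.2.2". SAP 2.2 lists these rates as a secondary endpoint.

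**The concern.** The rule that closes the window and the rule that dates a finding meet on the same day. An event whose onset is the end-of-trial visit itself is not before that visit, and it is plainly not before the first dose either. The SAP presents only the two classes, so such an event has no place in the section 10.2 output.

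This would be a small wording matter if few events could land on that day. But for a subject followed to a pregnancy scan, the end-of-trial visit is the visit at which a silent loss or a vanished sac is first seen. It is also when the closing examinations and blood samples are taken. At stake are the count by type for a named secondary endpoint, and the causality, intensity and seriousness of any event identified at the closing visit.

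**Working it through.** No stated figure is in question, so the check sets the rules side by side.

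**1. Do the scan and the end-of-trial visit fall on the same day?** Because of the second antibody sample, protocol 6.9 allows end-of-trial assessments no earlier than 19-28 days after the last FSH dose. Days from last dose to scan = (last dose to trigger) + (trigger to retrieval) + (retrieval to transfer) + (transfer to scan). Trigger 0-1 day after the last dose is an assumption. Retrieval at 36 h ± 2 h is taken as 1-2 days. Transfer is 3 days after retrieval.

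- 5-6 week scan: 0 + 1 + 3 + 35 = 39 to 1 + 2 + 3 + 42 = 48 days.
- 10-11 week scan: 0 + 1 + 3 + 70 = 74 to 1 + 2 + 3 + 77 = 83 days.

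Both lie beyond day 28, so antibody sampling does not force a later, separate visit. For a subject who attends as scheduled, the scan and the end-of-trial assessments share one day.

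**2. Which class does an event dated on that day enter?** Pre-treatment requires onset before the first dose, which fails. Treatment-emergent requires onset before the end-of-trial visit, which also fails. The SAP 10.2 fallback covers only events whose timing relative to IMP cannot be established. Here the date is known, so it does not apply.

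**3. Which events are affected, and where else are they reported?**

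| Event | Onset date | In SAP 10.2 tables, read literally | Elsewhere in the SAP |
|---|---|---|---|
| Silent loss first seen at the 5-6 week scan, no vital pregnancy | Scan = end-of-trial | No | 10.9 early losses (total, by interval); 9.3 ectopic or intrauterine type |
| Silent loss first seen at the 10-11 week scan | Scan = end-of-trial | No | 10.9 early losses (total, by interval) |
| Vanishing twin first documented at the 10-11 week scan | Scan = end-of-trial | No | No dedicated table |
| Significant examination change | End-of-trial | No | 10.11.1 and 10.11.2 shift tables and listings |
| Significant laboratory or vital-sign change | End-of-trial | No | 10.4 and 10.11.4 summaries, shift tables and flags |
| Loss with earlier symptoms or menses | Earlier | Yes | As above |

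For vanishing twins, protocol 8.3.6 requires that the disappearance of a sac beside one remaining viable fetus be documented by ultrasound. Table 6-1 schedules two pregnancy scans. A sac seen at the first and gone by the second is first documented at the second, which is the end-of-trial visit for every vital pregnancy. Barring an unscheduled scan, all such cases are excluded, whatever their rate.

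**4. How does the SAP word neighbouring windows?** SAP 7.3 counts a medication as concomitant unless it began after the end-of-trial visit, so that day is in. SAP 10.4 treats end-of-trial laboratory data as treatment-emergent. A significant end-of-trial laboratory value is therefore treatment-emergent as a result but not as an adverse event.

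**5. How many events?** The documents give no loss rate. To show how open the number is, take 32.2% × 1,000 = 322 ongoing pregnancies. Assume a fraction L of βhCG-positive subjects is lost and a fraction s of those losses is first seen at a scheduled scan. Events = s × (322/(1 − L) − 322).

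- L = 10%, s = 25%: 0.25 × (358 − 322) = 0.25 × 36 = 9.
- L = 30%, s = 75%: 0.75 × (460 − 322) = 0.75 × 138 ≈ 104.

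A range of 9 to 104, both arms together and resting on assumed inputs, is not an estimate. It shows only that the documents do not determine the number.

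**The case against.** **The intended meaning is probably inclusive.** SAP 10.2 groups events by the start of IMP, so the first dose is the real divide and the end-of-trial visit may only mark the close of collection. Adverse events are recorded at that visit (protocol 6.9), and SAP 10.9 promises the incidence of all four pregnancy outcomes. Reading the window as running up to and including the visit reconciles these passages, and a programmer might well do so. That stands as a view of intent. It does not change the written rule, and the inclusive wording in SAP 7.3 and 10.4 shows that the SAP says so where it means it.

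**Much of the information survives.** This stands. Besides the outputs tabulated under working, biochemical pregnancies can be approximated by subtracting clinical pregnancies from positive βhCG results. Losses between vital and ongoing pregnancy are essentially spontaneous abortions. Vanishing twins are covered only in part, through the number of sacs with heart beat (SAP 9.3) and the pregnancy types at the two assessments (SAP 10.9).

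**The protocol's frequency tables may still be produced.** Protocol 9.7.3 plans them, SAP section 12 does not list them as dropped, and the table shells are a separate document. That is possible, but SAP 10.9 itself names only the adverse event summaries for these four outcomes.

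**Onset of a loss is not always the scan date.** Correct: the general rule is first sign or symptom, and protocol 8.3.6 lets reported menstruation establish a biochemical pregnancy. The point is confined to events first identified at the closing visit.

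**Conclusion.** Read literally, the definition leaves events first identified at the end-of-trial visit in neither class. They therefore drop out of the SAP 10.2 tables and listings on which SAP 10.9 relies. The substantive loss is vanishing twins, and with them the causality, intensity and seriousness coding of findings made at that visit. This assumes that subjects attend as scheduled, that end-of-trial assessments are done at the scan visit, and that no unscheduled scan comes first.

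Three stronger readings might be inferred, and the documents support none of them:

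- **Absence from all adverse event output.** SAP 10.7 and 10.8 are not expressly limited to treatment-emergent events, and the underlying results are largely reported elsewhere.
- **A definite number of lost events.** No loss rate or silent fraction is given.
- **Bias between arms.** The same window applies to both, and nothing shows a differential effect.

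The primary analysis and the sample size are unaffected. The contradiction is worth settling before the safety tables are programmed.

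**What to change.** 1. In SAP 10.2 and protocol 9.7.3, define treatment-emergent as onset after the start of IMP up to and including the end-of-trial visit. State that this covers findings from samples and examinations taken at that visit, and apply the same closing point to the worsening clause.
2. In SAP 10.9, restore the frequency tables planned in protocol 9.7.3 for biochemical pregnancy, spontaneous abortion, ectopic pregnancy and vanishing twins. Derive them from the recorded pregnancy outcomes, so that the counts do not depend on adverse event dating.

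The cost is one sentence in each document and one derivation with its tables. No new data, visits or assessments are needed.
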